#### **4.4 Risks associated with participation in the clinical investigation.**

The potential risks associated with participation in the clinical study are considered to be similar with those risks associated with other IAD skin protectant products used for the treatment of IAD in the hospital routine. According to the manufacturer's Instructions for Use one potential risk could be an allergic reaction to any of the ingredients of Cavilon Advanced Skin Protectant. The liquid of Cavilon Advanced Skin Protectant is highly flammable and care should be taken not to apply the product in the presence of heat-emitting devices or open flames (e.g. candle) until the barrier film has dried.

#### **4.5 Possible interactions with concomitant medical treatments.**

The following precautions with regard to concomitant medical treatments are described in the manufacturer's Instruction for Use:

Precautions:

- Skin absorption and the effectiveness of topical medications (including: antimicrobials, antifungals, and analgesics) may be reduced or prevented by the presence of the Cavilon Advanced Skin Protectant.
- Use of other barrier products, ointments, creams or lotions may significantly reduce the effectiveness of the product.
- The product can increase the adhesion of some adhesive products (e.g. tape), particularly in the first few days of use. When removing an adhesive product, it is important to exercise care and follow the Instructions for Use.

 
3M Deutschland GmbH [name] [name], Germany
	
Clinical Investigational Plan / Protocol
 
3M Confidential
	
CLIN-PROT-EU-05-293312 Version: 3 Status: Release Release Date: 01/30/2018 07:29:52 AM CST Page 19 of 60

--	--	---

#### 4.6 Steps that will be taken to control or mitigate the risks.

The following steps will be taken to control or mitigate the risks:

- All investigators are selected with regard to their profound expertise regarding IAD management.
- Research study nurses will be trained on the manufacturer's Instruction for Use.
- Specific inclusion/exclusion criteria are defined to enroll appropriate patients
- The skin of the patients will be assessed daily during the study

Risks are minimized at the clinical site through:

- Compliance with the manufacturer's Instruction for Use
- Compliance with this study protocol
- Close monitoring of the patient's status during study participation

#### 4.7 Risk-to-benefit rationale

Cavilon Advanced Skin Protectant was tested in an open label, non-randomized prospective study in the United States (ClinicalTrials.gov. Identifier: NCT02724449; publication free text available [32]). The purpose of the study was to evaluate the efficacy of Cavilon Advanced Skin Protectant at managing severe skin breakdown associated with incontinence. The sample comprised 16 patients; inclusion criteria were: patients older than 18 years, cared for in the intensive care unit of a level I trauma center hospital or in long-term care facilities in the northeast region of the United States, and had incontinence-associated dermatitis (IAD). Twelve of the patients had epidermal skin loss and 4 had severe redness. The IAD score improved in 13 of 16 patients, remained unchanged in 1 patient, and deteriorated in 2 patients. The median percent improvement in the skin assessment instrument was 96% (p = .013). Four of the patients with epidermal skin loss had complete reepithelialization of the skin surface with 4 to 6 applications of the skin protectant, and 5 had substantial improvement. The 4 patients with severe red skin returned to healthy normal skin with 2 to 4 skin protectant applications. Substantial pain reduction was reported by all 9 patients who reported pain at enrollment. No adverse events associated with the skin protectant application were reported during data collection.

The product is currently tested against zinc oxide paste in a randomized controlled trial in the United States (ClinicalTrials.gov Identifier: NCT02570139).

 3M Deutschland GmbH [name] [name], Germany	Clinical Investigational Plan / Protocol  3M Confidential	CLIN-PROT-EU-05-293312 Version: 3 Status: Release Release Date: 01/30/2018 07:29:52 AM CST Page 20 of 60
--	---	---

Based on the reported clinical data it is concluded that the product meets the claims according to the manufacturer's Instructions for Use, and that potential undesirable clinical effects and risks can be controlled and are acceptable, when weighed against the benefits of IAD therapy.

## 5. Objectives and hypotheses of the clinical investigation

### 5.1 Objectives

The objective of the study is to assess the effects of 3M Cavilon Advanced Skin Protectant in comparison to the local IAD care regimes of Western European hospitals. Due to the exploratory design of the study the objectives are not divided into primary and secondary objectives. The study is designed as an exploratory study to learn more about the effect size of certain variables such as healing outcome when compared to different local IAD care regimes and will consider the medical routine of Western European hospitals regarding IAD care under real-world circumstances. Due to the exploratory design no formal a priori hypothesis is defined. The results of the study will be used to examine the feasibility of a potential subsequent confirmatory RCT.

### 5.2 Hypothesis

The study is of exploratory design and no formal a priori hypothesis is defined.

### 5.3 Claims and intended performance

The claims and intended performance described in the manufacturer's Instructions for Use were supported with laboratory and clinical data generated in the United States. This study will test the product performance under the medical routine of European hospitals. The performance will be compared to local IAD management regimes.

### 5.4 Anticipated risks and adverse device effects

According to the warnings described in the manufacturer's Instructions for Use an allergic reaction to Cavilon Advanced Skin Protectant would constitute an anticipated adverse event in this study.

 3M Deutschland GmbH [name] [name], Germany	Clinical Investigational Plan /  Protocol  3M Confidential	CLIN-PROT-EU-05-293312 Version: 3 Status: Release Release Date: 01/30/2018 07:29:52 AM CST Page 21 of 60
--	--	---

## 6. Statistical consideration

### 6.1 Statistical design, method and analytical procedures

This study is designed as an exploratory RCT to measure possible effects of Cavilon Advanced Skin Protectant in the management of IAD when compared to local IAD care regimes (please refer to the study endpoints for more details). The treatment will be integrated into the daily medical routine of the hospitals to assess the effects in comparison to the local IAD care under real-world circumstances.

All quantitative data such as demographics, IAD history, IAD skin assessments, pain assessments will be summarized with descriptive statistics. In general continuous variables will be summarized using the following standard descriptive summary statistics: number of observations, arithmetic mean, standard deviation, minimum, median, maximum. Categorical variables will be displayed by means of frequency tables and, where appropriate, shift tables. The statistical analyses will be based on analysis sets defined as follows:

Full analysis set including safety:

The full/safety analysis set will include all patients enrolled

Per-protocol analysis set:

The per-protocol analysis set – being a subset of the full analysis set – will only include patients who complete treatment of at least five days. Additionally, patients with major protocol violations which may have an impact on efficacy evaluation will be excluded from the per-protocol analysis set.

The determination of major protocol violations which may have an impact on the statistical analyses and the resulting definition of analysis sets will be performed prior to start of any statistical analyses. A summary of the number of patients per analysis set will be given and reasons for exclusion of a patient from an analysis set will be listed.

The statistical analysis will be performed using the software package SAS® version 9.3 or higher (SAS Institute Inc., Cary, NC 27513, USA).

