### 6.2 Sample size

Due to the exploratory design no formal a priori hypothesis is defined. The intention is to learn more about the effect size of certain variables such as healing outcome when

3M 3M Deutschland GmbH [name] [name], Germany	Clinical Investigational Plan / Protocol  3M Confidential	CLIN-PROT-EU-05-293312 Version: 3 Status: Release Release Date: 01/30/2018 07:29:52 AM CST Page 22 of 60
--	---	---

compared to different local IAD care regimes in hospitals. The results of the study will be used to examine the feasibility of a potential subsequent confirmatory RCT.

Total: n = 60 patients

Stratum 1: n = 30 IAD 1A patients

(persistent redness without clinical signs of infection)

Stratum 2: n = 30 IAD 2A patients

(skin loss without clinical signs of infection)

The patients will be allocated 1:1 to either Cavilon Advanced Skin Protectant or hospital IAD standard care regime.

Each site is expected to recruit 10 IAD 1A and 10 IAD 2A patients for the study:

5 IAD 1A patients allocated to Cavilon Advanced Skin Protectant

5 IAD 1A patients allocated to hospital IAD care

5 IAD 2A patients allocated to Cavilon Advanced Skin Protectant

5 IAD 2A patients allocated to hospital IAD care

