### **6.3 Level of significance and power**

Not applicable

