### **6.4 Expected drop-out rate**

The sample size of 60 patients includes an anticipated drop-out rate of 20%.

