## 7.3 Endpoints

Due to the exploratory design of the study the endpoints are not divided into primary and secondary endpoints.

The following endpoints are defined for the study with regards to the comparison of Cavilon Advanced Skin Protectant and local IAD hospital care:

1. Number and percentage of patients completely healed (skin free of any IAD signs, including erythema)
2. Number and percentage of patients improved with regard to IAD category
3. Number and percentage of patients with 100% re-epithelialization of skin loss (skin loss: skin is moist, as the epidermal layer is missing)
4. Time to complete healing or reduction in IAD category
5. Protection of IAD category 1 patients from developing IAD category 2
6. Prevention with regard to IAD recurrence
7. Material cost based on product utilization such as type of products, frequency of application and days of treatment
8. Use of resources involved in the IAD therapy
9. Nursing time to clean up incontinence and to administer IAD treatment products
10. Pain scores with regard to cleansing procedure and application of IAD product (Wong-Baker FACES® Pain Rating Scale: assessment only for cognitively healthy patients according to the judgement of the study nurse)

 3M Deutschland GmbH [name] [name], Germany	Clinical Investigational Plan /  Protocol  3M Confidential	CLIN-PROT-EU-05-293312 Version: 3 Status: Release Release Date: 01/30/2018 07:29:52 AM CST Page 25 of 60
--	--	---

11. Number and percentage of patients with adverse events and the nature of each adverse event

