## 11. Assessment of effects/performance

### 11.1 Effect/performance parameters

Cavilon Advanced Skin Protectant in comparison to IAD Hospital Standard Care

IAD Healing/Improvement

- ✓ IAD severity category according to the Ghent Global IAD Categorization Tool [33] evaluated by the research study nurses on-site
  - IAD 1A: persistent redness without clinical signs of infection
  - IAD 1B: persistent redness with clinical signs of infection
  - IAD 2A: skin loss without clinical signs of infection
  - IAD 2B: skin loss with clinical signs of infection
  - IAD free: skin free of any IAD signs, including erythema
- ✓ IAD affected area in cm^2 evaluated by the research study nurses on-site
  - Total IAD affected area inclusive signs of erythema (measurement sheet estimate)
  - Area affected by IAD skin loss (measurement sheet estimate)
- ✓ IAD severity category according to the GLOBIAD Tool evaluated by the blinded assessor based on the photographs of the study area that is defined as the sacral region going down to the upper thighs, bordered approximately 5 cm below the gluteal fold.
  - IAD 1A: persistent redness without clinical signs of infection
  - IAD 1B: persistent redness with clinical signs of infection
  - IAD 2A: skin loss without clinical signs of infection
  - IAD 2B: skin loss with clinical signs of infection
  - IAD free: skin free of any IAD signs, including erythema
- ✓ IAD affected area in cm^2 traced by the blinded assessor based on the photographs of the study area.
  - Total IAD affected area inclusive signs of erythema (software calculation in cm^2)
  - Area affected by IAD skin loss (software calculation in cm^2)
- ✓ Time to healing in days
  - Number of days to achieve improvement in severity category according to the GLOBIAD Tool or days until complete healing without any signs of erythema

 
3M Deutschland GmbH [name] [name], Germany
	
Clinical Investigational Plan / Protocol
 
3M Confidential
	
CLIN-PROT-EU-05-293312 Version: 3 Status: Release Release Date: 01/30/2018 07:29:52 AM CST Page 35 of 60

--	--	---

Prevention of IAD Deterioration and Recurrence

- ✓ IAD severity category according to the Ghent Global IAD Categorization Tool evaluated by the research study nurses on-site and the blinded assessor based on the photographs of the study area.

Pain Assessment

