(only for cognitively healthy patients according to the judgement of the study nurse)

- ✓ IAD pain scores according to the Wong-Baker FACES® Pain Rating Scale at the start and the end of the study (pain scores 0 – 10)
- ✓ Pain scores according to the Wong-Baker FACES® Pain Rating Scale associated with the incontinence cleanup (pain scores 0 – 10)
- ✓ Pain scores according to the Wong-Baker FACES® Pain Rating Scale associated with the IAD product application (pain scores 0 – 10)

Material cost and resource use

- ✓ Material cost based on the information with regard to the utilization of certain IAD care products such as cleansing products, skin protectants building up the moisture barrier, IAD wound dressings or other products, their used quantity, application frequency and duration of use.
- ✓ Resources involved in the IAD therapy (e.g. number of nurses or specialists/ number of interventions)

IAD Nursing Time

- ✓ Time taken to clean up incontinence in minutes
- ✓ Time taken to apply the skin protectant building up the moisture barrier and other products that might be needed to prepare the skin ( e.g. lotions to dry-out lesions before applying the skin protectant building up the moisture barrier)

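### No baseline-adjusted arm difference is specified for blinded traced area or pain, although both have Day 01 values, and traced area is missing from the 7.3 endpoint list

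*Combined protocol and SAP*

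**What the plan says.** Section 6.1 gives the whole stated analysis of continuous data: "All quantitative data such as demographics, IAD history, IAD skin assessments, pain assessments will be summarized with descriptive statistics", by means of six summary statistics. Frequency tables and, where suitable, shift tables are planned for categorical data. No change from baseline, covariate model, between-arm difference or confidence interval is named. Section 6.3 on significance and power reads "Not applicable".

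Day 01 values exist for both outcomes. Section 7.4 schedules pain before and during cleansing on Day 01. Section 11.2 sends the Day 01 photographs to the blinded reader, who traces total IAD area and skin-loss area; software converts the tracings to cm². Section 11.1 lists area "traced by the blinded assessor based on the photographs of the study area" as an effect parameter, and also pain on the Wong-Baker FACES "Pain Rating Scale at the start and the end of the study".

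Section 7.3 opens with "The following endpoints are defined for the study with regards to the comparison" of the device with local care and then lists 11 endpoints. Pain is number 10. None is an area endpoint.

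Randomisation is stratified by IAD category 1A or 2A (7.2), which is also the planned subgroup (6.9). Section 6.8 promises an SAP before data lock; no separate SAP text is in the supplied document.

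**The concern.** The stated purpose is to learn effect sizes for a possible confirmatory trial (5.1, 6.2). Estimation is therefore the objective, and six summary statistics per arm do not by themselves give a comparative estimate. Starting area and starting pain are natural predictors of the later values. Neither is a stratification factor, so with groups this small the arms can differ on them by chance. If end values alone are compared, part of that difference appears as treatment effect or hides it, and precision available from data already collected is lost.

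Traced area also deserves a clear place in the plan. The study nurses cannot be blinded (7.2), and traced area is the only continuous outcome measured by a blinded rater. The plan provides training, tracing and software to measure it, but 7.3 does not mention it.

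**Working it through.** **The plan's own numbers.** "Total: n = 60 patients" and "The patients will be allocated 1:1 to either Cavilon Advanced Skin Protectant or hospital IAD standard care regime" give 30 per arm, and 15 per arm in each category of 30. The bookkeeping agrees: 3 sites × 20 = 60; 2 strata × 30 = 60; 3 sites × 2 categories × 2 arms × 5 = 60. Section 6.4 says "The sample size of 60 patients includes an anticipated drop-out rate of 20" per cent, so 60 × 0.8 = 48 are expected to complete: 24 per arm, or 12 per arm per category. No effect size, SD, alpha or power is stated, so there is no power calculation to reproduce.

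**Chance imbalance in a baseline mean.** With n per arm, the SE of the difference is SD × √(2/n) and the 95% range is ±1.96 × √(2/n) SD.

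| n per arm | SE (SD units) | 95% range | P(imbalance > 0.3 SD) | P(imbalance > 0.5 SD) |
|---|---|---|---|---|
| 30 | 0.258 | ±0.51 | 25% | 5% |
| 24 | 0.289 | ±0.57 | 30% | 8% |
| 15 | 0.365 | ±0.72 | 41% | 17% |
| 12 | 0.408 | ±0.80 | 46% | 22% |

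These figures are for a baseline variable unrelated to the stratification factor.

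**What carries through.** Let r be the correlation between the Day 01 and end values, with equal SDs. The documents do not give r; 0.3, 0.5 and 0.7 are assumptions. A baseline imbalance D moves the end-value difference by r × D and the change-score difference by −(1 − r) × D. It moves the adjusted difference by about 0. For D = 0.5 SD:

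| r | End value | Change score | Adjusted |
|---|---|---|---|
| 0.3 | +0.15 | −0.35 | about 0 |
| 0.5 | +0.25 | −0.25 | about 0 |
| 0.7 | +0.35 | −0.15 | about 0 |

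**Precision.** Relative to the end-value variance, the change score has variance 2(1 − r) and the adjusted estimate 1 − r². Adjustment therefore removes r²: 9%, 25% and 49%. The 95% half-widths, in SD units, are:

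| n per arm | End value | Change score (r = 0.3 / 0.5 / 0.7) | Adjusted (r = 0.3 / 0.5 / 0.7) |
|---|---|---|---|
| 30 | 0.51 | 0.60 / 0.51 / 0.39 | 0.48 / 0.44 / 0.36 |
| 15 | 0.72 | 0.85 / 0.72 / 0.55 | 0.68 / 0.62 / 0.51 |

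Allowing for the estimated slope by a factor √(1 + 1/(2n − 4)), the adjusted half-widths at 15 per arm become 0.70, 0.63 and 0.52. At r = 0.3 the gain within a category is therefore slight. Below r = 0.5 the change score is less precise than the end value.

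**Simulation check.** In 20,000 simulated trials with 30 per arm and no treatment effect, at each r, the mean raw difference was within 0.004 SD of zero. The slope on the imbalance was 0.30, 0.49 and 0.70 for end values, −0.70, −0.51 and −0.30 for change scores, and between −0.01 and 0.00 for the adjusted estimate.

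**The case against.** A reader might infer that the plan restricts the analysis to raw values. It does not say so. Section 6.1 introduces its list as the general approach, 11.1 names pain at start and end, and the SAP could add change scores or a model. What stands is that no estimate using the Day 01 value is specified. Shift tables for categorical data do not supply one for cm² or pain scores.

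A reader might also infer that imbalance passes in full into the comparison, or that the effect size and SD handed to the next trial would be wrong. Neither follows. Only the fraction r carries through, the raw difference is unbiased over randomisations, and the raw end-value SD is a valid planning quantity. A 0.5 SD imbalance is also a tail event with 30 per arm (about 5%), though less so within a category (about 17%). Stratification controls baseline differences that run between 1A and 2A, notably in skin-loss area, but not those within a category.

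Other objections limit the gain:
- Healed patients have zero area. In the earlier 16-patient study described in 4.7, all 4 patients with severe redness returned to normal skin and median improvement was 96%. Similar healing here could push r well below 0.5.
- The blinded end reading is at Day 21 or discontinuation, so follow-up time varies. Because early leavers are also photographed, the 20% drop-out need not reduce the area data to 12 per arm per category.
- Pain is scored only in cognitively healthy patients, so 60 is an upper limit. The scale has six ordered faces, and a linear model is an approximation.

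Finally, the trial is exploratory, with no hypothesis. That removes any concern about a formal test, but not the case for the most informative estimate. Day 01 data and listings would allow adjustment later. However, with D = 0.5 SD and r = 0.5 the choice between end value and change score alone moves the result by 0.50 SD (+0.25 against −0.25), which is a reason to fix the choice in advance.

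**Conclusion.** The point holds as an omission. The plan names no between-arm estimate that uses the Day 01 value for blinded traced area or pain, and 7.3 does not agree with 11.1 on traced area. The consequence is lost precision and sensitivity to chance imbalance in this one trial, not bias or an invalid result. Imbalance of up to ±0.51 SD at 30 per arm, or ±0.72 SD at 15 per arm within a category, lies within the 95% range. The variance saved by adjustment is about 9% to 49% for r from 0.3 to 0.7. That range rests on an assumed r, equal SDs and a linear relation, and is smaller if many end areas are zero. It is worth correcting because effect sizes are what the trial is meant to deliver.

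**What to change.** In 6.1 and the SAP, keep the raw summaries. Beside them, report the device-minus-control difference at end of study with 95% CI, from a model containing the patient's own Day 01 value and IAD category. Do this for:
- blinded traced total area;
- blinded traced skin-loss area, in the 2A stratum only (where category is constant and drops out of the model);
- cleansing/IAD pain, in scorable patients only, with their number reported.

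Analyse area on a square-root or other scale that accepts zero; a plain log is undefined for healed patients. Do not use a plain change score as a substitute. State that the end reading is taken at Day 21 or discontinuation. The nurse-estimated area is recorded in cm² bands and is better kept in ordinal or shift-table form.

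Add blinded traced area, relative to Day 01, to the 7.3 list so that it agrees with 11.1.

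The cost is a few sentences in the SAP and one line in 7.3, with no new data, visits or patients. The small downside is that patients without a Day 01 value drop out of the model; their number should be reported.

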**3M Confidential**

CLIN-PROT-EU-05-293312

Version: 3

Status: Release

Release Date: 01/30/2018

07:29:52 AM CST

Page 12 of 60

	
Total: n = 60 patients
 
Stratum 1: n = 30 IAD 1A patients          (persistent redness without clinical signs of infection)
 
Stratum 2: n = 30 IAD 2A patients          (skin loss without clinical signs of infection)
 
The patients will be allocated 1:1 to either Cavilon Advanced Skin Protectant or hospital IAD standard care.
 
Each site is expected to recruit 10 IAD 1A and 10 IAD 2A patients:          5 IAD 1A patients allocated to Cavilon Advanced Skin Protectant          5 IAD 1A patients allocated to hospital IAD care          5 IAD 2A patients allocated to Cavilon Advanced Skin Protectant          5 IAD 2A patients allocated to hospital IAD care

Randomization	
Stratified randomization with regard to different IAD categories:          Stratum 1: IAD 1A (50% of the patients)          Stratum 2: IAD 2A (50% of the patients)
 
The patients will be allocated 1:1 to either Cavilon Advanced Skin Protectant or hospital IAD standard care

Geography	United Kingdom, Germany, Belgium
# Sites	
3 sites (1 in UK, 1 in Germany, 1 in Belgium)
 
# patients per site:          20 patients per site (10 IAD 1A patients and 10 IAD 2A patients)
 
Depending on the recruitment rate the sponsor reserves the right to allow for competitive recruitment or to add additional sites. Each site includes at least 10 patients.

Study Length	10 months including an enrollment period of 9 months.
Data Analysis Planned	
Intention-to-treat analysis (performance/safety)          Per-protocol analysis (performance)          All quantitative data will be summarized with descriptive statistics.

 
3M Deutschland GmbH [name] [name], Germany
	
Clinical Investigational Plan / Protocol
 
3M Confidential
	
CLIN-PROT-EU-05-293312 Version: 3 Status: Release Release Date: 01/30/2018 07:29:52 AM CST Page 13 of 60

--	--	---

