## 7.2 Randomization and blinding

The random numbers will be generated by computer. The randomization is stratified with respect to two different IAD severity categories according to the Ghent Global IAD Categorization Tool [33; appendix 24.2]. Stratum 1 is defined as IAD category 1A (persistent redness without clinical signs of infection) and Stratum 2 as IAD category 2A (skin loss without clinical signs of infection). The strata are of same sizes (50:50 ratio). The participants will receive either Cavilon Advanced Skin Protectant or the local hospital IAD care products within the same stratum. Due to the obvious differences between the comparative hospital IAD care products and the study device, the study nurses cannot be blinded. A blinded assessor will assess the healing outcome based on the photographs of the study area that is defined as the sacral region going down to the upper thighs, bordered approximately 5 cm below the gluteal fold.

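### The trial aims to learn an effect size, but the stated analysis names no between-arm estimate, no confidence interval and no method for censored healing times

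*Combined protocol and SAP*

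**What the plan says.** **Purpose.** Section 5.1 says the study is to "learn more about the effect size of certain variables such as healing outcome when compared to different local IAD care regimes". It adds: "The results of the study will be used to examine the feasibility of a potential subsequent confirmatory RCT". The synopsis and section 6.2 give the same aim, and section 7.3 defines the endpoints as a comparison of the device with local care.

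**Method.** The synopsis row on planned data analysis reads: "All quantitative data will be summarized with descriptive statistics". Section 6.1 gives the detail. Continuous variables get "number of observations, arithmetic mean, standard deviation, minimum, median, maximum". For the rest, "Categorical variables will be displayed by means of frequency tables", with shift tables added where they fit.

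**Strata.** Section 7.2: "The randomization is stratified with respect to two different IAD severity categories". Section 6.9 names the same two categories, 1A and 2A, as subgroups.

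**Deferred detail.** Section 6.8 promises an SAP before data lock but says nothing of its content. Section 6.3 marks significance level and power as not applicable. Section 6.11 says missing first observations of re-epithelialisation or healing will be imputed, without a method.

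**Follow-up.** Under section 9.6 a patient can leave before Day 21, for example on discharge, count as having completed the study, and not be followed afterwards. Endpoint 4 in section 7.3 is a time to healing or category improvement.

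**The concern.** An effect size is a contrast between arms. The stated outputs describe each variable; none is a contrast, and none carries a standard error or interval. The lack of a formal hypothesis explains why there is no test. It does not explain why there is no estimate with its precision, which is the main product of an exploratory trial.

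Two things are at stake:

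- Whoever judges the feasibility of a confirmatory trial would see two percentages side by side, with nothing in the planned output to show how far apart chance alone could put them.
- For the time endpoint the stated summaries are unsuitable as well as incomplete. A mean or median needs a value for every patient, and a patient discharged unhealed has none.

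**Working it through.** **1. The plan's own figure.** The sample size of 60 is consistent with itself: 3 sites × 20 = 60; 2 categories × 30 = 60; and 60 × (1 − 0.20) = 48 after the drop-out in section 6.4. With no assumed rate, SD, power or target interval width, 60 has no precision basis to reproduce. The available group sizes are:

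- full analysis set (all enrolled): 60/2 = 30 per arm, 30/2 = 15 per arm within a category;
- after 20% drop-out: 48/2 = 24 per arm, 24/2 = 12 per arm within a category.

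**2. Precision of a difference in healing proportions.** The documents give no healing rate, so rates are assumed. The 95% half-width is 1.96 × √[p₁(1−p₁)/n + p₂(1−p₂)/n]. With both rates at 50% it becomes 1.96 × √(0.5/n). The last column shows the range over assumed pairs from 30% vs 20% up to 50% vs 50%.

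| n per arm | Calculation at 50% | Half-width at 50% (points) | Range (points) |
|---|---|---|---|
| 30 | 1.96 × √0.01667 | 25.3 | 22 to 25 |
| 24 | 1.96 × √0.02083 | 28.3 | 24 to 28 |
| 15 (one category) | 1.96 × √0.03333 | 35.8 | 31 to 36 |
| 12 (one category) | 1.96 × √0.04167 | 40.0 | 34 to 40 |

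As an illustration, suppose 60% vs 30% heal. At 30 per arm the Wilson limits are 42.3% to 75.4% and 16.7% to 47.9%. The Newcombe interval for the 30-point difference is then

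- lower: 30 − √(17.7² + 17.9²) ≈ +5 points;
- upper: 30 + √(15.4² + 13.3²) ≈ +50 points.

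At 15 per arm the same method gives −5 to +56 points. Two percentages in a frequency table show none of this.

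**3. What stratifying does.** Assume the category healing rates are the same in both arms, with equal category sizes. The ratio of the stratified to the unstratified variance formula is the mean of p(1−p) over categories, divided by p̄(1−p̄).

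- Rates 70% and 40%: [(0.21 + 0.24)/2] / (0.55 × 0.45) = 0.225/0.2475 = 0.909; √0.909 = 0.953, an interval about 5% shorter.
- Rates 80% and 40%: [(0.16 + 0.24)/2] / (0.60 × 0.40) = 0.20/0.24 = 0.833; √0.833 = 0.913, about 9% shorter.

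With balanced strata the Mantel-Haenszel and crude differences coincide, so the point estimate does not change. The stratified formula gives an interval that matches the way patients were randomised.

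**4. The time endpoint.** Set endpoint 4 beside section 9.6. A patient discharged unhealed before Day 21 has a healing time known only to exceed the last assessment. Averaging only the observed healing days leaves that patient out and favours fast healers. Entering the day of discharge as a healing day records an event that did not happen. If length of stay differs between arms, either shortcut distorts the comparison. No censoring rule or time-to-event method is stated, and a valid contrast cannot be rebuilt afterwards from a mean, SD and median.

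**The case against.** The best defence has four parts.

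- **An SAP is promised.** Section 6.8 puts it before data lock, section 6.1 says its list of summaries applies in general, and section 7.3 frames the endpoints as a comparison. This stands as far as it goes: the SAP could fill the gap. Its content is not in the document, however, so what can be shown is that the protocol does not name the measures, not that they will never be produced.
- **An estimate is recoverable.** A reader might infer that no between-arm estimate can come out of this plan. That goes too far. If tables are shown by arm, which section 6.1 does not say but section 7.3 implies, a crude risk difference and interval follow from the counts, and a mean difference follows from n, mean and SD. What remains true is that none is planned. A stratum-adjusted or time-to-event contrast would not follow from the arm-level summaries alone.
- **Category is not ignored.** A reader might also infer that the analysis disregards the randomisation strata or pools over them. Section 6.9 specifies both categories as subgroups, and nothing says that tables will be pooled. The gap is the missing contrast and interval, by category and combined.
- **The later use is limited.** The protocol says the results will inform the feasibility of a confirmatory trial. It does not say that trial will be sized on the observed difference.

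The imputation statement in section 6.11 does not answer the censoring problem. It gives no method, and a patient who left unhealed has no first healing observation to recover.

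**Conclusion.** The point holds in this form: for an aim stated as an effect size, the protocol names no between-arm measure, confidence interval or stratum-adjusted estimate, and no method for healing times that are cut off by discharge. The last is the more serious part, because the stated summaries would mislead there. For the binary endpoints the missing information is large: half-widths of about 25 to 28 points overall and 36 to 40 points within a category, if 50% heal. All healing rates used here are assumptions; other assumed pairs give 22 to 28 points overall and 31 to 40 within a category.

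The variance ratios of 0.909 and 0.833 should not be read as precision bought by a stratified analysis. Stratified randomisation already delivers that precision; the stratified formula stops the interval from overstating the variance. The exploratory design remains a sound reason for having no hypothesis test. This should be changed, but it does not call the design into question.

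**What to change.** Add to section 6.1, or to the SAP before data lock:

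- For each binary endpoint, the risk difference (device minus local care) with a 95% confidence interval, overall stratified by IAD category and separately within each category. Mantel-Haenszel overall and Newcombe within category would serve; other standard choices would too.
- For time to healing or improvement, Kaplan-Meier curves by arm, with unhealed patients censored at their last skin assessment. Add a category-stratified between-arm contrast with a 95% interval, for example the difference in restricted mean time up to the latest day supported in both arms. Early discharge may leave too little follow-up to go to Day 21.
- A statement that early discharge or withdrawal may be informative, so the censored analysis is read with that caution.

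No p-values or significance level are needed. The cost is a paragraph and a few tables and figures. The daily skin assessments already supply the event and censoring days, so there is no new data collection and no change to the sample size.
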